3.1. Inclusion Criteria

Subject must meet all of the following applicable inclusion criteria to participate in this study:

1. Male or female \geq 18 years of age at time of consent.
2. Histologically-confirmed malignant mesothelioma not amenable to curative surgery and who have received at least one pemetrexed-containing chemotherapy regimen.
3. Eastern Cooperative Oncology Group (ECOG) performance status of 0 or 1.
4. Adequate hepatic function within 28 days prior to study registration defined as meeting all of the following criteria:
 - total bilirubin < 1.5 mg/dL (25.65 μ mol/L) OR direct bilirubin \leq ULN for subjects with total bilirubin levels > 1.5 mg/dL (except subject with Gilbert's Syndrome, who can have total bilirubin < 3.0 mg/dL)
 - aspartate aminotransferase (AST) $\leq 3 \times$ ULN or $\leq 5 \times$ ULN for subjects with known hepatic metastases
 - alanine aminotransferase (ALT) $\leq 3 \times$ ULN or $\leq 5 \times$ ULN for subjects with known hepatic metastases
5. Adequate hematologic function within 28 days prior to study registration defined as meeting all of the following criteria:
 - hemoglobin ≥ 8 g/dL, subjects requiring transfusion will not be eligible to start study
 - and absolute neutrophil count (ANC) $\geq 1.5 \times 10^9/L$
 - and platelet count $\geq 100 \times 10^9/L$
6. Adequate renal function within 28 days prior to study registration by either of the following criteria:
 - serum creatinine ≤ 1.5 times the ULN, or creatinine clearance (measured via 24-hour urine collection) ≥ 40 mL/minute (that is, if serum creatinine is > 1.5 times the ULN, a 24-hour urine collection to calculate creatinine clearance must be performed)
 - subject's urinary protein is $\leq 1+$ on dipstick or routine urinalysis (UA; if urine dipstick or routine analysis is $\geq 2+$, a 24-hour urine collection for protein must demonstrate < 1000 mg of protein in 24 hours to allow participation in this protocol)

7. Adequate coagulation functioning within 28 days prior to study registration defined by either of the following criteria:
 - INR \leq 1.5, and a partial thromboplastin time (PTT) (PTT/aPTT) $< 1.5 \times$ ULN (unless receiving anticoagulant therapy)

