 - Subjects on full-dose anticoagulation must be on a stable dose (minimum duration 14 days) of oral anticoagulant or low molecular weight heparin (LMWH). Patients receiving warfarin must be switched to low molecular weight heparin and have achieved stable coagulation profile prior to first dose of protocol therapy. For heparin and LMWH there should be no active bleeding (that is, no bleeding within 14 days prior to first dose of protocol therapy) or pathological condition present that carries a high risk of bleeding (for example, tumor involving major vessels or known varices).
8. Subjects must be willing to undergo a CT-guided biopsy (i.e., image-guided percutaneous lung biopsy) to obtain tumor tissue within 28 days before initiation of treatment and after 4 cycles (8 weeks) of treatment.
9. Women of childbearing potential (WOCP) must be willing to use birth control as outlined in Section 5.6.2.
10. Men who are not surgically or medically sterile must agree to use contraception as outlined in Section 5.6.2.
11. Measurable disease, defined as at least 1 tumor that fulfills the criteria for a target lesion according to modified RECIST 1.1 criteria, and obtained by imaging within 28 days prior to study registration.
12. Prior intracavity cytotoxic or sclerosing agents (including bleomycin) is acceptable.
13. Radiation therapy must be completed $>$ 28 days before study registration, and the measurable disease must be outside of the radiation port.
14. Pemetrexed-containing chemotherapy must be completed $>$ 28 days before study registration.
15. Must provide written informed consent and HIPAA authorization approved by an Institutional Review Board (IRB). NOTE: HIPAA authorization may be included in the informed consent or obtained separately.
16. All previous toxicity resolved to Grade 1 or less.

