3.2. Exclusion Criteria

1. Any Grade 3-4 GI bleeding within 3 months prior to study registration.
2. History of deep vein thrombosis, pulmonary embolism, or any other significant thromboembolism (venous port or catheter thrombosis or superficial venous thrombosis are not considered “significant”) during the 3 months prior to study registration.
3. Any arterial thromboembolic events, including but not limited to myocardial infarction, transient ischemic attack, cerebrovascular accident, or unstable angina, within 6 months prior to study registration.
4. Cirrhosis at a level of Child-Pugh B (or worse), or cirrhosis (any degree) with a history of hepatic encephalopathy, or clinically meaningful ascites resulting from cirrhosis. Clinically meaningful ascites is defined as ascites from cirrhosis requiring diuretics or paracentesis.
5. Uncontrolled or poorly-controlled hypertension (>160 mmHg systolic or > 100 mmHg diastolic for >4 weeks) despite standard medical management.

6. Prior history of GI perforation/fistula (within 6 months of study registration) or risk factors for perforation.
7. Serious or nonhealing wound, ulcer, or bone fracture within 28 days prior to study registration.
8. Active brain metastases or carcinomatous meningitis. Subjects with neurological symptoms must undergo a head CT scan or brain MRI to exclude brain metastasis. Subjects with previously treated brain metastases may participate provided they are stable (without evidence of progression by imaging for at least four weeks prior to the first dose of study drugs and any neurologic symptoms have returned to baseline), have no evidence of new or enlarging brain metastases, and are not using steroids for at least 14 days prior to study registration. This exception does not include carcinomatous meningitis, which is excluded regardless of clinical stability.
9. Major surgery within 28 days prior to study registration
10. Subcutaneous venous access device placement within 7 days prior to study registration.
11. Elective or planned major surgery to be performed during the course of the clinical trial.
12. Is receiving chronic antiplatelet therapy, including aspirin, nonsteroidal anti-inflammatory drugs (NSAIDs, including ibuprofen, naproxen, and others), dipyridamole or clopidogrel, or similar agents. Once-daily aspirin use (maximum dose 325 mg/day) is permitted.

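### Inclusion 7 allows full-dose anticoagulation with an oral agent or LMWH, but its 14-day no-bleeding condition covers only heparin and LMWH

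*Combined protocol and SAP*

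**What the plan says.** The second bullet of item 7 in Section 3.1 deals with subjects on full-dose anticoagulation. They "must be on a stable dose (minimum duration 14 days) of oral anticoagulant or low molecular weight heparin (LMWH"). The bullet then requires anyone on warfarin to move to LMWH and to have a stable coagulation profile before first dose.

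The bleeding condition comes next: "For heparin and LMWH there should be no active bleeding (that is, no bleeding within 14 days prior to first dose of protocol therapy"). The same sentence also rules out, for heparin and LMWH users, pathology that carries a high bleeding risk.

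Item 7 of the synopsis eligibility list repeats the permission for oral agents and LMWH. It gives no bleeding condition and refers the reader to Section 3.1. Section 5.5 on concomitant medications adds no bleed-free requirement.

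**The concern.** The list of permitted agents and the list of agents under the bleeding condition do not match. The permission names oral agents and LMWH. The condition names heparin and LMWH. A subject who stays on a non-warfarin oral anticoagulant is permitted by the first and not covered by the second, and the documents give no reason for the difference.

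What is at stake is subject safety at entry. Section 10.1.5 lists hemorrhage among the important identified risks of ramucirumab, and every subject is asked to undergo image-guided percutaneous biopsies. On treatment, Table 2 in Section 6.3.1 requires ramucirumab to stop for bleeding only at Grade 3-4, and holding for a persistent or intolerable Grade 2 event is at the physician's discretion. Entry is therefore the natural place for a uniform rule on recent lower-grade bleeding.

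**Working it through.** The plan states no figure to reproduce, so the check is mainly a reading of the eligibility criteria.

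**Step 1: does another criterion supply a bleed-free window for oral-agent users?**

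- Inclusion 5 works through blood counts and transfusion ("subjects requiring transfusion will not be eligible to start study"). It has no bleeding window.
- Inclusion 16 is "All previous toxicity resolved to Grade 1 or less". A resolved bleed passes.
- Exclusion 1 is "Any Grade 3-4 GI bleeding within 3 months prior to study registration". It is limited by site and grade.
- Exclusion 7 is "Serious or nonhealing wound, ulcer, or bone fracture within 28 days prior to study registration". It catches some sources of bleeding, not bleeding as such.
- Exclusions 20 and 21 cover major vessel invasion, cavitation and, in 21, hemoptysis in the 2 months before first dose. They are limited by site.
- Exclusion 24 covers high-bleeding-risk pathology in all subjects. It has no time window and does not concern actual bleeding.
- Exclusion 22 is investigator discretion. It has no window.

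Exclusion 24 carries the second half of the item 7 sentence over to everyone. Nothing does the same for the first half, the 14-day condition.

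**Step 2: a test case.** Take a Grade 2 nosebleed or hematuria 7 days before the planned first dose, now resolved, with adequate hemoglobin, no transfusion and no high-risk lesion. On LMWH, 7 is less than 14, so the item 7 condition fails. On a stable non-warfarin oral agent, none of the listed criteria applies except exclusion 22.

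**Step 3: how many subjects?** The documents give no rate of anticoagulant use or of recent bleeding, so no probability can be computed. Exclusion 2 ("History of deep vein thrombosis, pulmonary embolism, or any other significant thromboembolism", within 3 months of registration) removes some of the people most likely to be on full-dose anticoagulation.

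**Step 4: what would the extended rule cost one subject?** Let d be the days from the bleed to the planned first dose, and assume no further bleeding.

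- Deferral = 14 - d. For d = 7 this is 14 - 7 = 7 days. For d = 0 it is 14 days, the maximum.
- An assessment with validity window W stays usable if it was taken no more than W - (14 - d) days before the original date.
- Baseline scan, W = 28 (Section 8.4): d = 7 gives 28 - 7 = 21 days; d = 0 gives 28 - 14 = 14 days.
- Baseline biopsy, W = 14 (synopsis treatment plan and Section 12.6): d = 7 gives 14 - 7 = 7 days; d = 0 gives 14 - 14 = 0 days.
- Cycle 1 labs, W = 7 (Section 7, footnote 13): d = 7 gives 7 - 7 = 0 days, so only labs drawn on the original date would stand.

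**The case against.** The strongest reply is that the gap is almost empty. Once severe GI bleeds, hemoptysis, wounds and ulcers, high-risk pathology, transfusion need and unresolved toxicity are removed, what is left is a resolved, mostly low-grade bleed in a subject on one class of drug, and the investigator can still refuse entry. Subjects not on anticoagulants have no general bleed-free window either. A bleed of a grade that would not force ramucirumab to stop on treatment is a weak ground for concern at entry. All of this stands, and it sets the size of the point. It does not explain why two permitted classes of full-dose anticoagulant are treated differently.

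A second objection is to extending the condition as it is written. It has no grade threshold and a percutaneous biopsy is required. If the biopsy is done within 14 days of first dose, almost any bleeding from it falls inside the no-bleeding window. Deferral then ages the biopsy, and a repeat biopsy risks a new bleed. This stands and is met by an exemption in the fix.

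A reader might go further and infer that LMWH users can also escape the condition, because the lead-in to item 7 reads "Adequate coagulation functioning within 28 days prior to study registration defined by either of the following criteria" and the INR/PTT bullet could be met instead. The documents do not support that. The INR/PTT bullet carries its own exception for those receiving anticoagulants, and the next bullet says subjects on full-dose anticoagulation must meet its terms. The natural reading is one bullet per population. Inclusion 6 uses the same loose lead-in for two plainly separate requirements, creatinine and urinary protein.

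**Conclusion.** The point holds as a minor safety gap in the wording of item 7. A subject on a stable non-warfarin oral anticoagulant with a recent resolved bleed can enter where the same subject on LMWH cannot, unless the investigator intervenes. The bleeds concerned are mostly low grade, and the subjects are few or none.

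This rests on reading the sentence literally, as limited to heparin and LMWH, and on the review of the other criteria above. It does not rest on any assumed rate of anticoagulant use or bleeding.

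A reader might infer some effect on the trial's evidence. There is none: the response-rate endpoint and the sample size do not depend on this criterion.

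**What to change.** In Section 3.1 item 7, replace the opening of the bleeding sentence, up to its parenthesis, with: *For all subjects on full-dose anticoagulation (oral agent, heparin or LMWH) there should be no active bleeding*. Keep the 14-day definition and the high-risk-pathology clause. Add one sentence: *Minor self-limited bleeding from the protocol-required biopsy does not count.* The synopsis needs no change, since it already points to Section 3.1. If the sponsor intends to treat oral agents differently, a stated reason would serve instead.

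The drafting cost is one phrase and one sentence. The operating cost is an occasional deferral, 14 days at most without further bleeding, with possible repeat Cycle 1 labs or a repeat baseline scan.

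The biopsy cost should not be assumed away. Inclusion 8 and Section 7 footnote 8 allow tissue up to 28 days before treatment, so a biopsy taken 14 days before the original date would be 14 + 14 = 28 days old after the longest deferral and still meet them. But the tissue-change objectives in Section 2.1.3 and the tissue analyses in Section 12.6 take baseline tissue from the 14 days before treatment. A deferred subject's biopsy could satisfy eligibility and still fall outside that baseline, so it cannot be said that no repeat would be needed.

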3.2. Exclusion Criteria

1. Any Grade 3-4 GI bleeding within 3 months prior to study registration.
2. History of deep vein thrombosis, pulmonary embolism, or any other significant thromboembolism (venous port or catheter thrombosis or superficial venous thrombosis are not considered “significant”) during the 3 months prior to study registration.
3. Any arterial thromboembolic events, including but not limited to myocardial infarction, transient ischemic attack, cerebrovascular accident, or unstable angina, within 6 months prior to study registration.
4. Cirrhosis at a level of Child-Pugh B (or worse), or cirrhosis (any degree) with a history of hepatic encephalopathy, or clinically meaningful ascites resulting from cirrhosis. Clinically meaningful ascites is defined as ascites from cirrhosis requiring diuretics or paracentesis.
5. Uncontrolled or poorly-controlled hypertension (>160 mmHg systolic or > 100 mmHg diastolic for >4 weeks) despite standard medical management.

6. Prior history of GI perforation/fistula (within 6 months of study registration) or risk factors for perforation.
7. Serious or nonhealing wound, ulcer, or bone fracture within 28 days prior to study registration.
8. Active brain metastases or carcinomatous meningitis. Subjects with neurological symptoms must undergo a head CT scan or brain MRI to exclude brain metastasis. Subjects with previously treated brain metastases may participate provided they are stable (without evidence of progression by imaging for at least four weeks prior to the first dose of study drugs and any neurologic symptoms have returned to baseline), have no evidence of new or enlarging brain metastases, and are not using steroids for at least 14 days prior to study registration. This exception does not include carcinomatous meningitis, which is excluded regardless of clinical stability.
9. Major surgery within 28 days prior to study registration
10. Subcutaneous venous access device placement within 7 days prior to study registration.
11. Elective or planned major surgery to be performed during the course of the clinical trial.
12. Is receiving chronic antiplatelet therapy, including aspirin, nonsteroidal anti-inflammatory drugs (NSAIDs, including ibuprofen, naproxen, and others), dipyridamole or clopidogrel, or similar agents. Once-daily aspirin use (maximum dose 325 mg/day) is permitted.
13. Known history of testing positive for human immunodeficiency virus (HIV) or known acquired immunodeficiency syndrome (AIDS). NOTE: HIV testing is not required.
14. Known history of testing positive for hepatitis B virus surface antigen (HBV sAg) or hepatitis C virus ribonucleic acid (HCV antibody), indicating acute or chronic infection. NOTE: Hepatitis B and Hepatitis C testing is not required.
15. Condition requiring systemic treatment with either corticosteroids (> 10 mg daily prednisone equivalents) or other immunosuppressive medications within 14 days of study drug administration. Inhaled or topical steroids and adrenal replacement doses > 10 mg daily prednisone equivalents are permitted in the absence of active autoimmune disease.
16. Active autoimmune disease that has required systemic treatment in the past 2 years (i.e. with use of disease modifying agents, corticosteroids or immunosuppressive drugs). Subjects are permitted to enroll if they have vitiligo, type I diabetes mellitus, residual hypothyroidism due to autoimmune condition only requiring hormone replacement, psoriasis not requiring systemic treatment, or conditions not expected to recur in the absence of an external trigger.
NOTE: Replacement therapy (e.g., thyroxine, insulin, or physiologic corticosteroid replacement therapy for adrenal or pituitary insufficiency, etc.) is not considered a form of systemic treatment.
17. Received a live vaccine within 30 days prior to the first dose of trial treatment. Examples of live vaccines include, but are not limited to: measles, mumps, rubella, chicken pox, yellow fever, rabies, BCG, and typhoid (oral) vaccine. Seasonal influenza vaccines for injection are generally killed virus vaccines and are allowed; however, intranasal influenza vaccines (e.g. Flu-Mist®) are live attenuated vaccines and are not allowed.
18. History of interstitial lung disease or active, non-infectious pneumonitis.
19. Female subject is pregnant or breast-feeding.

NOTE: Women of childbearing potential (WOCOP) must have a negative pregnancy test (either serum β -HCG with a sensitivity of 50 mIU/ml or urine dipstick within 24 hours of study registration).

NOTE: Women are not considered to be of childbearing potential if they meet at least one of the following: 1) surgically sterilized, or 2) postmenopausal (a woman who is \geq 45 years of age and has not had menses for greater than 1 year), or 3) not heterosexually active for the duration of the study. See section 5.6.2.

20. Major blood vessel invasion or significant intratumor cavitation.
21. If they experience hemoptysis (defined as bright red blood or \geq $\frac{1}{2}$ teaspoon) within 2 months prior to first dose of protocol therapy or with radiographic evidence of intratumor cavitation or has radiologically documented evidence of major blood vessel invasion or encasement by cancer.
22. Any condition that, in the opinion of the investigator, might jeopardize the safety of the subject or interfere with protocol compliance.
23. Any mental or medical condition that prevents the subject from giving informed consent or participating in the trial.
24. Any pathological condition that carries a high risk of bleeding (for example, tumor involving major vessels or known varices.)
25. Known hypersensitivity to nivolumab or ramucirumab or any of their components.
26. Known history of active tuberculosis.
27. Received prior therapy with an anti-PD-1, anti-PD-L1, anti-PD-L2, anti-CD137, or anti-Cytotoxic T-lymphocyte-associated antigen-4 (CTLA-4) antibody (including ipilimumab or any other antibody or drug specifically targeting T-cell co-stimulation or checkpoint pathways).
28. No prior malignancy is allowed except for adequately treated basal cell or squamous cell skin cancer, *in situ* cervical cancer, localized Gleason \leq grade 7 prostate cancers. Subjects with other solid tumors treated curatively and without evidence of recurrence for at least 3 years prior to enrollment may be eligible for study after discussion with the sponsor-investigator
29. Treatment with any investigational agent within 28 days prior to study registration. The subject must have recovered from the acute toxic effects of the regimen.

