	
8. Subjects must be willing to undergo a CT-guided biopsy (i.e., image-guided percutaneous lung biopsy) to obtain tumor tissue within 28 days before initiation of treatment and after 4 cycles (8 weeks) of treatment.
 
9. Women of childbearing potential (WOCP) must not be pregnant (confirmed by a negative pregnancy test: a serum β-HCG with a sensitivity of 50 mIU/ml within 24 hours of study registration or urine dipstick) or breast-feeding. Women are not considered to be of childbearing potential provided they meet at least one of the following: 1) surgically sterilized, or 2) postmenopausal (a woman who is ≥ 45 years of age and has not had menses for greater than 1 year), or 3) not heterosexually active for the duration of the study.
 
10. Women of childbearing potential (WOCP) must be willing to birth control as outlined in Section 5.6.2.
 
11. Men who are not surgically or medically sterile must agree to use contraception as outlined in Section 5.6.2.
 
12. Measurable disease, defined as at least 1 tumor that fulfills the criteria for a target lesion according to modified RECIST 1.1 criteria and obtained by imaging within 28 days prior to prior to study registration.
 
13. Prior intracavity cytotoxic or sclerosing agents (including bleomycin) is acceptable.
 
14. Radiation therapy must be completed > 28 days of study registration, and the measurable disease must be outside of the radiation port.
 
15. Pemetrexed-containing chemotherapy must be completed > 28 days of study registration.
 
16. No prior malignancy is allowed except for adequately treated basal cell or squamous cell skin cancer, in situ cervical cancer, localized Gleason \leq grade 7 prostate cancers. Subjects with other solid tumors treated curatively and without evidence of recurrence for at least 3 years prior to enrollment may be eligible for study after discussion with the sponsor-investigator

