5.6.2. Contraception

Ramucirumab and nivolumab may have adverse effects on the composition of sperm or on a fetus *in utero*. Investigators shall counsel WOCBP, and male participants who are sexually active with WOCBP, on the importance of pregnancy prevention and the implications of an unexpected pregnancy, the potential of fetal toxicity occurring due to transmission of study drug, present in seminal fluid, to a developing fetus, even if the participant has undergone a successful vasectomy or if the partner is pregnant.

Women of childbearing potential (WOCBP) must be willing to use two methods of birth control. The two birth control methods can be either two barrier methods or a barrier method plus a hormonal method to prevent pregnancy. WOCBP should begin using birth control from the screening visit, throughout the study period, and up to 5 months following the last dose of study drugs. Total abstinence for the same study period is an acceptable alternative. Women of non childbearing potential or considered highly unlikely to conceive are defined as 1) surgically sterilized, or 2) postmenopausal (a woman who is ≥ 45 years of age and has not had menses for greater than 1 year will be considered postmenopausal), or 3) not heterosexually active for the duration of the study.

Men who are not surgically or medically sterile must agree to use an acceptable method of contraception. Male subjects with female sexual partners who are pregnant, possibly pregnant, or who could become pregnant during the study must agree to use condoms with spermicide from the date of the first dose of study drug, throughout the study period, and through 3 months after the last dose of study drug. Total abstinence for the same study period is an acceptable alternative.

The following are considered adequate barrier methods of contraception: diaphragm, condom (by the partner), copper intrauterine device, sponge, or spermicide. Appropriate hormonal contraceptives will include any registered and marketed contraceptive agent that contains an estrogen and/or a progestational agent (including oral, subcutaneous, intrauterine, or intramuscular agents).

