7 STUDY CALENDAR & EVALUATIONS

Study Day [Cycle = 14 days]	Screen	Cycle 1	Cycle 2 +	Safety Follow up ¹⁴	Safety Follow up ¹⁴	Long Term Follow Up ¹⁵
	-28 days	Day 1 (± 3)	Day 1 (± 3)	30 days (±7)	90 days (±7)	Q 3 months (±14 days)
REQUIRED ASSESSMENTS						
Informed Consent/HIPAA auth.	X					
Medical History ¹	X					
Physical Exam	X	X	X	X		
Vital Signs including ECOG PS ²	X	X	X	X		
AE Assessment and Con Meds	X	X	X	X	X	
LABORATORY ASSESSMENTS						
Blood Chemistries ³	X	X ¹³	X	X		
Thyroid Function Testing ⁴	X	X ¹³	X	X		
PT/INR and aPTT	X	X ¹³	X	X		
Platelets, ANC & Hgb	X	X ¹³	X	X		
Urinalysis	-7d ⁵	X ¹³	X			
Pregnancy Test for WOCP ⁶	X	-24h	X ⁶			
DISEASE ASSESSMENT						
CT or MRI chest, abdomen/pelvis ⁷	X		X			X
CT or MRI Brain, if indicated ⁷	[X]					
TREATMENT						
Nivolumab		X	X			
Ramucirumab		X	X			
CORRELATIVE STUDIES						
CT-guided biopsy ⁸	X		X ⁸			
Whole Blood for Somatic Baseline ⁹		X				
Serum for soluble PD-L1 analysis ⁹		X	C5D1			
BANKING SAMPLES						
Whole Blood ¹⁰ - Optional		X				
Serum and Plasma ¹¹ - Optional		X		X		
Unstained Slides ¹² - Optional		X	X ¹²			
FOLLOW UP						
Survival status, additional cancer therapy						X

Footnotes:

1. Medical history to include demographics, prior treatments, radiation and surgical history. Other information obtained during the medical history includes: Smoking history to include: amount, frequency, start and stop dates of cigarette, cigar and pipe usage. A question about how the patient heard about the study. Prior genetic or biomarker testing results will be required if available.
2. Vital signs to include BP, HR, weight, height (screening) only. In addition, ECOG performance status should be obtained.
3. Blood Chemistries to include: sodium, potassium, blood urea nitrogen (BUN), serum creatinine (or GFR; see 3.1.7), calcium, albumin, ALT, AST, bilirubin, alkaline phosphatase (ALK), total protein, glucose.
4. Thyroid studies will be obtained every 3 cycles (about 6 weeks) starting with Cycle 4 (\pm 7 day window). The type of testing performed (TSH, T3 free vs direct, or T4 free vs direct) should be per local standards.
5. Within 1 week of study registration. If urine dipstick or routine analysis is $\geq 2+$, a 24-hour urine collection for protein must demonstrate < 1000 mg of protein in 24 hours to allow participation in this protocol.

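### Intended abstinence during the study removes a fertile woman from the childbearing-potential group, so neither entry pregnancy test is required of her

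*Combined protocol and SAP*

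**What the plan says.** Section 3.2, exclusion 19, rules out any subject of whom it is true that "Female subject is pregnant or breast-feeding". Its first note then says that women of childbearing potential "must have a negative pregnancy test" around registration. Its second note takes a woman out of that group if she meets any one of three conditions: sterilisation, menopause as the protocol defines it, "or 3) not heterosexually active for the duration of the study".

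Synopsis item 9 carries the same third condition ("3) not heterosexually active for the duration of the study"). Section 5.6.2 repeats the list under a slightly wider label: "Women of non childbearing potential or considered highly unlikely to conceive are defined as" the same three conditions.

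In Section 7 the calendar row is titled "Pregnancy Test for WOCP". It is marked at screening, in the 24 hours before Cycle 1, and from Cycle 2 on. Footnote 6 to that row describes the two entry tests and adds repeat testing every four weeks.

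On the reason for testing, Section 5.6.2 says that the two drugs "may have adverse effects on the composition of sperm or on a fetus". Section 5.6.3 takes a subject who becomes pregnant off study treatment at once.

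**The concern.** The first two conditions are facts about fertility that hold on the day of entry. The third is a statement about what a woman will or will not do after entry. It can justify not asking her to use contraception, because it addresses the chance of conceiving on study. It cannot show that she is not already pregnant, because it says nothing about the weeks before registration.

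The plan uses one definition for both purposes. A fertile woman who will not be heterosexually active on study is therefore excused from the test as well as from contraception. What is at stake is fetal exposure to both antibodies from the first dose in a pregnancy that exclusion 19 was meant to keep out of the trial. No statistical quantity is involved.

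**Working it through.** No figure in the plan needs reproducing. The check is to trace the definition through each test requirement.

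1. **Who leaves the group.** Exclusion 19, synopsis item 9 and Section 5.6.2 use the same three conditions. Exclusion 19 and synopsis item 9 say expressly that one of them is enough, so the third is sufficient alone for a premenopausal, non-sterilised woman.

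2. **Who must be tested.** Exclusion 19 and synopsis item 9 ask for the registration test only from women of childbearing potential. The calendar row has the same limit in its title. Footnote 6 is worded generally, but it annotates that row and does not extend it.

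3. **Putting the two together** (required entry tests):
   - fertile, heterosexually active on study: 2 (screening or registration; within 24 hours of the first dose)
   - fertile, not heterosexually active on study: 0
   - sterilised or postmenopausal: 0

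   The second and third rows get the same treatment, although only the third describes women whose condition bears on whether they are pregnant at entry.

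4. **Whether anything else requires a test of her.**
   - Exclusion 22 is at the investigator's discretion and needs a reason for suspicion.
   - The closing text of Section 5.6.2 deals with reliable use of contraception and with informing subjects of fetal risk.
   - Section 11.3.4 depends on pregnancies being reported spontaneously.
   - The physical examination and adverse-event review on Day 1 of each cycle, and the CT or MRI scans, may give a chance to notice a pregnancy, but none is a pregnancy test.
   - The four-weekly tests belong to the same restricted row, so they do not reach her either.

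5. **Size.** Let k be the number of women classed only under the third condition. The required entry tests now missing are 2 × k. The documents give no age or sex distribution, so k is unknown. At k = 0 nothing is missing, at k = 1 two tests are missing, and at k = 3 six. The arithmetical ceiling of 2 × 35 = 70 is not realistic in this population.

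6. **Tests on treatment** (needed only to cost one form of the fix). With 52 cycles of 14 days and no delays, the last dose falls on day 1 + 14 × 51 = 715, which is week 102. Tests at weeks 4, 8, …, 100 number 100 / 4 = 25.

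**The case against.** The strongest reply is that the affected woman is very rare. She must have previously treated mesothelioma, be premenopausal and not sterilised, have conceived before entry without knowing it, and not be heterosexually active afterwards. A known pregnancy already excludes her, and clinical contact every two weeks gives some chance of recognition. The label in Section 5.6.2 also covers women thought unlikely to conceive, so the third condition may be a deliberate low-risk class. All of that stands as to frequency. It does not supply a test, and a low chance of conceiving on study is a different matter from the chance of being pregnant at entry.

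Four stronger readings are tempting, and the documents do not support them.

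- **That the plan admits pregnant women.** It does not. The bar in exclusion 19 covers every female subject; the gap is limited to pregnancies nobody has recognised.
- **That the plan flatly contradicts itself on her status.** Section 5.6.2 tells women of childbearing potential that "Total abstinence for the same study period is an acceptable alternative" to contraception, which suggests that an abstinent fertile woman stays in the group and is tested. But being totally abstinent and not being heterosexually active overlap without being the same, since a woman may be sexually active only with women. The result is an ambiguity that sites could settle either way. It neither closes the gap nor amounts to a full contradiction.
- **That the exposure can be put at four doses of each drug** (days 1, 15, 29 and 43, before the week-8 scan). The scan is not a pregnancy test, so nothing in the plan makes it the point of detection. The documents support no dose count.
- **That she also needs the four-weekly tests.** Those look for conception on treatment. They are not needed to close a gap at entry.

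**Conclusion.** The point holds as a narrow safety gap in the eligibility rules. For each woman classed only under the third condition, required entry pregnancy tests fall from 2 to 0, and no other provision requires one before the first dose.

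This rests on reading footnote 6 as limited by the row it annotates, which agrees with exclusion 19. It also rests on sites doing only what is required; a site may of course test anyway. That very few of the 35 subjects would be affected is a judgement from the disease setting, not a figure in the documents.

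The response-rate endpoint, the sample size and every planned analysis are untouched. The change is still worth making, because the harm guarded against is serious and the remedy is a test the protocol already uses.

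**What to change.** **Preferred.** In exclusion 19, synopsis item 9 and calendar footnote 6, require the existing negative tests (screening or registration, and within 24 hours of the first dose) from every woman who is neither surgically sterilised nor postmenopausal, whatever her sexual activity. Keep the third condition, but let it waive only the contraception requirement and the four-weekly tests on treatment. The footnote should say expressly that the entry tests apply beyond the group named in the row title.

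**Equivalent for the entry gap.** Delete the third condition in all three places and reword the alternative to contraception in Section 5.6.2 as abstinence from heterosexual intercourse through 5 months after the last dose. The rewording is essential. With deletion alone, a fertile woman sexually active only with women would join the childbearing-potential group without being totally abstinent, and would have to accept two contraceptive methods to meet inclusion 9.

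**Cost.** The preferred form adds two urine or serum tests for each of very few women. The second form adds up to 25 four-weekly tests per woman if she completes 52 cycles. Either needs a minor protocol amendment. Section 15.1 has the IRB informed under local requirements but does not say that notification alone is enough for an eligibility change, and the trial runs under an IND (Section 11.4.1), so the amendment would have to be handled there too.
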